8 STATISTICAL ANALYSES

8.1 Sample Size and power considerations

HBsAg loss is the primary endpoint; the trial will compare the rate of HBsAg loss in patients three years after cessation of nucleos(t)ide analogues with the rate of HBsAg loss in patients treated with pegylated interferon after cessation of nucleos(t)ide analogues. Only one published study provides an estimate of the rate of HBsAg loss in patients who stopped treatment after 4 years of nucleos(t)ide analogues which was 10% at 1 year,18% at 2 years and 24% at 3 years. A similar study reported by Berg (EASL 2015) confirmed the 10% HBsAg loss reported at 1 year. In the present study we will recruit some patients who have had treatment with nucleos(t)ide analogues for only 3 years and we will therefore use a conservative assumption for the rate of HBsAg loss in this group at 15% at 2 years and 20% at 3 years.

There is no data on the rate of HBsAg loss in patients who have been treated with nucleos(t)ide analogues and subsequently been treated with pegylated interferon. In a trial of pegylated interferon for naïve HBeAg negative hepatitis infection 42.4% had lost HBsAg at the end of follow up if the level of HBV DNA had been <70 IU/ml at the end of treatment. As this is an exploratory study we have assumed that the rate of HBsAg loss in this group will be 30% at 2 years and 40% at 3 years. This increment would represent the very significant clinical benefit which would justify the use of interferon (with associated side effects) in this group of patients.

A trial with 90% power to detect a difference in HBsAg loss between these groups (40% vs 20%) at the P < 0.05 threshold would require 109 subjects in each arm. Therefore allowing for ~10% withdrawal / dropout in each arm we will aim to recruit 120 subjects to each arm; a total of 240 patients in total. If either arm is discontinued after the pilot, then there will still be at least 80% power in comparison with an alternative trial arm in the post pilot participants.

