Two recent papers have addressed the issue of finite therapy in patients with HBeAg negative chronic HBV infection (7,8). The original paper by Hadziyiannis and colleagues assessed nucleos(t)ide withdrawal after a minimum of four years' treatment in a group of patients infected with HBV genotype D. These patients were allowed to undergo a virological flare and were followed up for 6 years. Eventually, 30% lost HBsAg. In contrast, Seto assessed the impact of nucleos(t)ide withdrawal in 184 patients infected with HBV genotypes B or C after two years of treatment. Hepatitic flares or resumption of high level viral replication was not permitted so the majority of patients returned to drug treatment. Interim analysis of a similar study presented by Berg et al at EASL 2015 confirmed the findings of Hadziyiannis up to one year after nucleos(t)ide cessation.

High level viral replication is associated with suppression of HBV-specific adaptive immune responses leading to viral persistence (9). Recent data suggest that there is partial restoration of immune responses in patients on long term treatment with antiviral drugs that suppress viral replication (10).

Interferon (standard or pegylated) has been used in the treatment of HBV for 20 years due to its antiviral and immunostimulatory effects. Combining interferon with nucleos(t)ide analogues as initial treatment for HBV infection does not improve therapeutic efficacy (4). However, a number of authorities now believe that sequential therapy (with or without a short break) may amplify immune responses due to the complementary immunological effects of IFN and nucleos(t)ide analogues on innate and adaptive arms respectively and result in increased rates of HBsAg clearance. Based on

NUC-B PROTOCOL Version 2.0 12 th Aug 2016	Sponsor Imperial College
--	-----------------------------

the above, we argue that it is timely to evaluate management options which may result in a cure of HBV, release patients from indefinite drug treatment and increase cost effective care.

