3 STUDY DESIGN

3.1 Pilot Phase

A pilot phase will be conducted at the beginning of the trial. This will consist of 50 patients recruited across 4 sites. Milestones within the pilot are based on numbers of patients recruited as well as safety aspects/numbers of exaggerated flares as shown in the flow diagram below. The pilot phase will be conducted according to the same protocol as the main trial and the pilot phase patients will count towards the overall trial sample size. Exaggerated flares are defined in Section 6.4 (i).

The milestones for the pilot phase are as follows:

- If the pilot phase fails to recruit 40 patients in 4 months then NIHR-EME will discontinue the study.
- If more than 40% of patients in either arm of the trial experience exaggerated flares by the end of the pilot phase then that arm will be discontinued. If this occurs in the interferon arm then the interferon arm will be modified to a control and combined interferon treatment protocol in which pegylated interferon is added to the nucleos(t)ide analogue for 16 weeks prior to cessation of therapy rather than leaving a gap between nucleos(t)ide analogues withdrawal and pegylated interferon treatment (and compared to the control arm still) see Figure 2. If this occurs in the control arm then the control arm will be switched to the interferon and combined interferon treatment protocol (and compared against the standard interferon arm) see Figure 3.
- If more than 60% of patients in the pilot experience exaggerated flares the trial will be discontinued.
- If more than 40% of patients in both arms experience exaggerated flare by the end of the pilot phase then the trial will be terminated if the DMEC and TSC recommend so.

A safety assessment will be made by the TSC and DMEC when all pilot patients will have completed initial screening, therapy gap and two months of interferon therapy. The trial will be assessed against the above milestones and a decision on the continuation of the trial made.

NUC-B	PROTOCOL Version 2.0 12 th Aug 2016	Sponsor Imperial College	
		impenal College	

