--	-----------------------------

By the end of the pilot phase, if more than 40% of patients in the control arm experience exaggerated flares then the control arm will be modified to the interferon and combined interferon treatment protocol in which pegylated interferon is added to the nucleos(t)ide analogue for 16 weeks from randomisation and prior to cessation of therapy. This will be compared against the standard interferon arm (used in the pilot phase). They will subsequently discontinue all antiviral medications. They will be followed up until 3 years after randomisation.

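### The claim of at least 80% power after dropping either arm is supported only if control is kept; with control replaced, Section 8.1 gives no effect to power

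*Protocol*

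**What the plan says.** Section 8.1 of the Protocol sets two rates for HBsAg loss. For withdrawal alone it uses a "conservative assumption for the rate of HBsAg loss in this group at 15% at 2 years and 20% at 3 years". For interferon given after nucleos(t)ide analogues, "we have assumed that the rate of HBsAg loss in this group will be 30% at 2 years and 40% at 3 years". The main calculation follows: "40% vs 20%) at the P < 0.05 threshold would require 109 subjects in each arm", at 90% power, and "allowing for ~10% withdrawal / dropout in each arm we will aim to recruit 120 subjects to each arm".

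The section then covers the case where the pilot leads to an arm being dropped: "If either arm is discontinued after the pilot, then there will still be at least 80% power in comparison with an alternative trial arm". The sentence ends by restricting this to patients randomised after the pilot. It names no rates for the comparison.

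Sections 3.1 and 5 describe two such cases.

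- **Interferon arm replaced (Figure 2).** Peginterferon is added to the nucleos(t)ide analogue (combined interferon) and compared with the existing control arm.
- **Control arm replaced (Figure 3).** Combined interferon takes the place of control. Section 5 says of it: "This will be compared against the standard interferon arm (used in the pilot phase").

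Table 1 (Section 3.3) puts 25 pilot patients in each arm of 120.

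**The concern.** The power sentence covers both cases with one figure, but the cases compare different things. With the interferon arm replaced, the 20% control arm remains, and the 40% vs 20% contrast can be carried over if combined interferon is assumed to do as well as sequential interferon. With control replaced, both arms receive interferon. The only rate that Section 8.1 gives for either of them is 40% for the standard schedule. A minimum power has no meaning without a difference to detect, and none is given.

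At stake is what the modified trial could be expected to show. A reader would take from Section 8.1 that it remains adequately powered whichever arm is lost. In the control-replaced case the post-pilot patients would also no longer address the contrast in Section 2.1, which is interferon after withdrawal against simple discontinuation.

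**Working it through.** **Inputs.** Rates of 20% and 40%, the 0.05 threshold, 90% power, 109 and 120 per arm, and about 10% dropout are from Section 8.1. The 25 pilot patients per arm are from Table 1, and 1:1 allocation is from Section 5.2. Sidedness is not stated; two-sided is assumed because it reproduces the plan's figure. No rate is given for combined interferon, so it is varied.

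**1. Reproduce 109 per arm.** Pooled two-proportion formula without continuity correction, with mean rate p̄ = 0.30:

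n = [1.960·√(2·p̄·(1−p̄)) + 1.282·√(p1(1−p1) + p2(1−p2))]² / (p1−p2)²

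= [1.960·√0.42 + 1.282·√(0.24 + 0.16)]² / 0.04 = 108.2, rounded up to **109**. The plan's figure is reproduced. A one-sided test would give 89, a continuity correction 119 and unpooled variance 106, so the two-sided pooled formula is used below.

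**2. Patients after the pilot.** 120 − 25 = 95 per arm. After 10% dropout, 95 × 0.9 = 85.5, about 86.

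**3. Power formula.** Power = Φ{ [|p1−p2| − 1.960·√(2p̄(1−p̄)/n)] / √[(p1(1−p1) + p2(1−p2))/n] }

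**4. Interferon arm replaced, control kept, 40% vs 20% (combined interferon assumed at 40%).**
- n = 95: (0.200 − 0.1303)/0.0649 = 1.07, power **86%**
- n = 86: (0.200 − 0.1370)/0.0682 = 0.92, power **82%**

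The stated minimum of 80% holds here.

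**5. Control arm replaced, standard interferon at 40%.** Worked example, 40% vs 60% with n = 86: (0.200 − 0.1494)/0.0747 = 0.68, power 75%.

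| Assumed combined rate | Power, 95 per arm | Power, 86 per arm |
|---|---|---|
| 20% | 86% | 82% |
| 30% | 30% | 28% |
| 40% | 5% (type I error only) | 5% |
| 50% | 28% | 26% |
| 55% | 54% | 50% |
| 60% | 79% | 75% |
| 65% | 94% | 91% |

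The same 20-point difference has less power at 40% vs 60% than at 40% vs 20% because the binomial variance is larger near 50%.

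**6. Rate needed for 80% power against 40%.** With 86 per arm, about 61% or more, or about 20.5% or less. With 95 per arm and no dropout, about 60% or more, or about 21% or less.

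**7. Size of trial for smaller gains.** For 80% power, 40% vs 50% needs 388 evaluable patients per arm, and 40% vs 55% needs 173.

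**The case against.** **A reader might infer that the 80% claim is false.** The documents do not support that. With no combined-interferon rate or target difference stated, power in the control-replaced case is undefined. A combined rate of 20% would give the same 82% as the control-kept case. The claim is therefore unsupported, and it fails for any combined rate between about 20.5% and 61% with 86 per arm. The 40% vs 60% shortfall without dropout is also marginal: 79% by the pooled formula, 80% by the unpooled one. The shortfall after dropout, 75% to 76%, does not depend on that choice.

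**A reader might infer that the plan pools pilot patients from a dropped strategy with those on its replacement**, since Section 3.1 says "the pilot phase patients will count towards the overall trial sample size" and Section 8.2 defines intention to treat as everyone randomised. But the power sentence itself limits the comparison to post-pilot participants, and the Section 3.1 line describes a pilot run under the same protocol as the main trial. This does not show an error.

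**A reader might infer that fewer than 95 per arm would remain**, because no pause in recruitment is stated while the pilot is assessed. The Protocol is silent on this, so any reduced figure would rest on assumed accrual and an assumed fixed total.

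**A reader might take "Combining interferon with nucleos(t)ide analogues as initial treatment for HBV infection does not improve therapeutic efficacy" as evidence about the combined arm.** It concerns initial therapy, not patients after years of suppression, and settles nothing about the rate here.

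It is also fair to say that this is one contingency, triggered only if more than 40% of control patients have exaggerated flares. The pilot rules in Section 3.1 turn on recruitment and flares, not on power. Losing the withdrawal comparison is the open consequence of a safety rule. All of that limits the weight of the point but does not supply the missing effect size.

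**Conclusion.** The point stands for one of the two cases that the sentence covers. The main sample size is correct, and the control-kept case is sound at 82% to 86% if combined interferon is taken as 40% against 20%. In the control-replaced case Section 8.1 states a minimum power with no effect behind it. Taking standard interferon at the Protocol's own 40% and about 86 evaluable per arm, a 10-point gain has 26% power and a 20-point gain 75%. Section 8.1 describes a 20-point gain over plain withdrawal as a very significant benefit; about 21 points more between two interferon schedules would be needed for 80%, and the Protocol nowhere assumes that.

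These figures rest on a two-sided 5% pooled test, 10% dropout, 95 patients per arm randomised after the pilot, and assumed combined-interferon rates.

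**What to change.** In Section 8.1, limit the at-least-80% statement to the case where the control arm is retained, and give its basis: 40% vs 20%, with 86% power at 95 per arm and 82% at about 86 per arm after 10% dropout.

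For the case where control is replaced, state the detectable difference instead. With standard interferon at 40% and about 86 per arm, power is 26% for 40% vs 50% and 75% for 40% vs 60%, and 80% needs a combined rate of about 61% or more, or about 20.5% or less. If the sponsor has a particular combined rate in mind, state it and give its power. Add that this comparison does not test the primary objective of interferon against simple withdrawal.

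The cost is a few sentences in an amendment and a less favourable stated power for one contingency. No patients, visits or procedures are added.

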5.2 Randomisation

Patients will be electronically randomised using the InForm eCRF online custom built database to the two management arms in equal proportions using variable block sizes. Randomisation will be stratified by gender and by HBsAg titre at baseline (< or \ge 2000 IU/mI) as this is the strongest predictor of clinical outcome in interferon based treatment and was found to be a predictor of outcome in the Hadziyannis study.

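### The at least 80% power claimed if an arm is replaced needs almost nobody to be randomised between the 50th pilot patient and the pilot decision, and the visible text states no such hold

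*Protocol*

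**What the plan says.** Protocol section 8.1 sizes the trial on HBsAg loss at 3 years of 40% versus 20%, with 90% power, and finds that this "at the P < 0.05 threshold would require 109 subjects in each arm". It continues: "allowing for ~10% withdrawal / dropout in each arm we will aim to recruit 120 subjects to each arm". Of the fallback, should either arm be discontinued after the pilot, it says that "there will still be at least 80% power in comparison with an alternative trial arm in the post pilot participants".

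Section 3.1 sets the pilot at 50 patients, who count towards the 240. Table 1 in section 3.3 shows 25 of them in each arm. Section 3.1 times the TSC and DMEC safety assessment at the point "when all pilot patients will have completed initial screening, therapy gap and two months of interferon therapy". If more than 40% of an arm has had exaggerated flares, that arm is replaced by an alternative regimen. The recruitment milestone reads: "If the pilot phase fails to recruit 40 patients in 4 months then NIHR-EME will discontinue the study". Section 5 gives the therapy gap as 4 weeks from randomisation. Section 5.2 allocates patients "to the two management arms in equal proportions using variable block sizes".

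**The concern.** Two sets of patients can be meant by post pilot. One is everyone after the 50th randomisation, which is 190 patients. The other is everyone randomised after the pilot decision, once the alternative arm exists. The fallback power needs the second set but comes out above 80% only at, or very near, the size of the first.

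The sets differ because the decision comes about three months after the 50th patient is randomised. Anyone randomised meanwhile goes to one of the two original arms. If an arm is then dropped, its interval patients have not received the alternative regimen and can say nothing about it. Interval patients in the continuing arm were not randomised against the alternative arm, so they are at best non-concurrent comparators.

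At stake is whether the replacement comparison has the power that 8.1 promises, and whether its analysis set is clear. Read literally, the post pilot label admits patients on a regimen that has been abandoned.

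**Working it through.** **Inputs from the protocol.** Rates 20% and 40%, threshold 0.05, about 10% dropout, 240 in total (8.1); pilot of 50, decision timing, 40 patients in 4 months (3.1); 4-week gap (5); 1:1 allocation (5.2). Sidedness is not stated. Two-sided is assumed because it reproduces the 109.

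**Assumption not in the protocol.** The randomisation rate between the 50th patient and the decision. I use 10 per month (40 ÷ 4, the pilot milestone pace) and show a range.

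**1. The protocol's own figure.** Pooled two-proportion test, no continuity correction:

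n = [z(0.975)·√(2·0.3·0.7) + z(power)·√(0.2·0.8 + 0.4·0.6)]² ÷ 0.2²

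For 90%: (1.960 × 0.6481 + 1.282 × 0.6325)² ÷ 0.04 = 108.2, so 109 per arm. It matches.

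**2. The fallback claim.** 240 − 50 = 190, or 95 per arm. Power = Φ[(0.2·√n − 1.960 × 0.6481) ÷ 0.6325].
- n = 95: Φ(1.074) = 85.9%.
- n = 95 × 0.9 = 85.5: Φ(0.916) = 82.0%.

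So at least 80% reproduces when all 190 enter the replacement comparison.

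**3. Length of the interval.** 4 weeks' gap plus two months of interferon is about 12 to 13 weeks after the last pilot patient is randomised.

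**4. How many can be lost.** For 80%: (1.960 × 0.6481 + 0.842 × 0.6325)² ÷ 0.04 = 81.2 evaluable per arm.
- With 10% dropout: 81.2 ÷ 0.9 = 90.2 recruited per arm, and 190 − 2 × 90.2 is between 9 and 10. Power is 80.1% with 9 lost and 79.9% with 10.
- With no dropout: 190 − 2 × 81.2 is between 27 and 28.

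Rounding up to whole patients at each step (82 evaluable, 92 recruited per arm, 184 in all) would give 6, but the excess over 9 is only rounding.

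**5. Power by number randomised in the interval (G).** Each arm loses G ÷ 2. The last column keeps the control arm's interval patients and assumes that the interferon arm is the one replaced.

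| G | Per arm left | No dropout | 10% dropout | 10% dropout, continuing controls kept |
|---|---|---|---|---|
| 0 | 95 | 85.9% | 82.0% | 82.0% |
| 10 | 90 | 83.9% | 79.9% | 81.0% |
| 14 | 88 | 83.1% | 79.0% | 80.6% |
| 20 | 85 | 81.8% | 77.6% | 79.9% |
| 28 | 81 | 79.9% | 75.5% | 79.0% |
| 69 | 60.5 | 67.4% | 62.7% | 72.7% |

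**6. Which row applies.** Twelve weeks is 12 × 12 ÷ 52 = 2.77 months. At 10 per month G is about 28; at 5 per month, about 14. At 25 per month, about 69; that last rate would need 10 sites open before the decision and recruiting at the pilot's per-site pace, so it is an outer bound.

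**The case against.** Several points on the other side are sound.

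- **The figure is not miscalculated.** A reader might infer an arithmetic error in 8.1. There is none: 82.0% with the stated dropout follows from 95 per arm.
- **A hold may exist.** A reader might infer that the plan lets recruitment run on. Section 3.1 refers to a flow diagram, and that diagram and Figures 1 to 3 are not shown. The text also allows a sequential reading, in which the pilot phase ends with the decision and the main trial of section 3.2 starts afterwards. Then post pilot means after the decision, and the 190 stands. The supportable statement is that the visible text states no hold and does not define post pilot.
- **Accrual is assumed.** The 40 in 4 months is a stopping threshold for the pilot, not a planned rate for the interval.
- **Some interval patients might be used.** If the interferon arm is replaced, controls from the interval are on the continuing regimen. Keeping them moves the crossing point from about 10 to about 20 (80.2% at 18) and gives 79.0% at 28. The price is a partly non-concurrent control group in an open-label comparison.
- **No text says that patients on an abandoned regimen would be analysed in the alternative arm.** The wording leaves that open but does not plan it, and a statistical analysis plan could settle the analysis set.

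These points limit the finding but do not remove it. The power claim, the decision timing and the replacement rule are all fixed in the protocol, and a later analysis plan cannot recover patients already randomised to a dropped arm. Recruiting beyond 240 would restore the numbers, but the text does not provide for it.

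**Conclusion.** The concern holds as a conditional one. The fallback power in 8.1 is right if randomisation stops at the 50th patient until the decision, and it has a margin of about 9 patients with 10% dropout. If recruitment continues at an assumed 10 per month, about 28 patients enter the original arms first, and the replacement comparison has about 75.5% power: 4 to 5 points below the stated floor. The shortfall is about 1 point if continuing controls are kept (79.0%) and negligible with no dropout (79.9%). The decline is gradual, so no sharp threshold should be read into it.

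This rests on 40% versus 20% also applying to the replacement comparison, a two-sided pooled test, the total staying at 240, and the interval accrual rate, which the protocol does not give. It matters only if one arm crosses the flare limit and is replaced. It should be put right, because a guaranteed minimum power is stated without the condition that it depends on.

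**What to change.** Choose one of the following and make 3.1 and 8.1 agree.

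1. **No pause intended.** In 8.1, define the replacement comparison as participants randomised concurrently after the pilot decision takes effect, in place of post pilot participants. Restate the power as a function of the number randomised in the interval: 82% with none, 79.9% with 10, about 76% at 10 per month, all with 10% dropout. Say how interval patients in each original arm will be reported. The cost is a few sentences and a lower stated power.
2. **Pause intended.** In 3.1, state that randomisation is held from the 50th pilot patient until the decision. The 82% then stands. The text change is one sentence, but the hold costs about 12 to 13 weeks of recruitment. The visit schedule puts baseline 4 to 12 weeks after screening, so some patients already screened when the hold starts may need rescreening.

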8.2 Data Analysis

(i) Primary Endpoint Analysis

This analysis will be performed primarily on an intention to treat (ITT) basis. The ITT population will be all subjects who have been randomized. Secondarily, a per protocol analysis will be performed. The per protocol population will be those confirmed to be eligible who have not resumed nucleos(t)ide analogues for patient/ physician preference and those, in the interferon arm, who have completed at least 8 weeks of interferon therapy. Rates of HBsAg loss will be compared between the two groups using logistic regression adjusting for the stratification factors HBsAg titre and centre. Results will be presented as odds ratios and their 95% confidence intervals.

(ii) Secondary outcomes

Secondary outcomes to be compared between the two groups will include the primary outcome assessed at one year and at two years from baseline. Kaplan-Meier plots will be produced to show the persistence of HBsAg. The plots will be supported by formal secondary analyses using Cox proportional hazards model methods

Achievement of the inactive carrier state (defined above) will be analysed using the same procedures as the primary outcome. A statistical analysis plan will be developed and approved by the Trial Steering committee prior to any regular analysis for reports to the Data Monitoring Committee. This plan will include details of the statistical methods to be used to analyse the outcomes, and describe the methods to undertake sensitivity analyses for handling missing data. The plan will contain conform with the Clinical Trials Unit standard operating procedures

(iii) Predictors of HBsAg Loss

Predictive factors for HBsAg loss will be explored using univariate and multivariate logistic regression analysis. Separate models will be fitted for the following variables: gender, age, duration of antiviral therapy, viral genotype, viral load pre-treatment, HBsAg titre, centre, peak ALT value post withdrawal, peak viral load post withdrawal, hepatic cccDNA, number of infected hepatocytes and ELISPOT counts. Odds ratios and their 95% confidence intervals produced from each of the models will be presented. Following this, a multivariate logistic regression analysis will be performed will include the variables that were statistically significant in the univariate analysis plus a variable for treatment group.

(iv) Safety analysis

The occurrence of exaggerated hepatitis flares, defined in Section 6.4, will be monitored in each arm of the trial and presented as part of the regular reporting to the Data Monitoring Committee.

